3.3 Study schedule summary

The study will consist of a screening period of up to 28-day, a window-of-opportunity 15-day treatment phase, an End of Treatment visit (EoT) (+ 1 day after the final dose of study treatment) and an End of Study (EoS) visit (28 days +/- 3 days after the final dose of study treatment).

3.3.1 Screening phase

During this phase, patient eligibility is determined, including the documentation of baseline characteristics. This phase will begin once the ICF is signed by the patient; procedures to be performed are described in **Appendix 1: Schedule of study assessments and procedures**.

Patients must have histologically confirmed ER[+]/HER2[-] primary invasive adenocarcinoma of the breast with locally analyzed and centrally confirmed Ki67 $\geq 10\%$ and tumor size $\geq 1.0\text{cm}$ in longest diameter by ultrasound.

A Ki67 score $\geq 10\%$ stained nuclei from the pre-treatment tumor tissue sample is required for eligibility. Ki67 score will be analyzed locally at the time of inclusion. *Patients with basal Ki67 $\geq 20\%$ will be assessed locally and centrally confirmed retrospectively and patients with 10-19% will be assessed centrally before inclusion.*

To assess eligibility, HER2, ER and PgR status will be locally determined on the most recent tumor biopsy acquired at baseline prior to beginning of study treatment.

All patients will be required to provide a pre-treatment tumor tissue sample and blood samples during screening, and a tumor biopsy sample and blood samples on Day 15 (+ 1 day) at the end of study treatment. If a diagnostic biopsy was performed maximum 8 weeks prior to initiation of study treatment, it can be used as a baseline sample for the Ki67 assessment. If post-treatment biopsy cannot be obtained within + 1 day from last day of treatment (15 days), treatment will be extended to 16 days and patients will be able to have surgery or biopsy the following day (be it D15 + 2 days).

One re-screening is allowed for patients that were screening failure. Patients have to re-consent Informed Consent Form (ICF) before any study procedure is done. At re-screening, study assessments and procedures can be omitted if were performed during the initial screening period within the specified time frames.

3.3.2 Treatment Phase and End of Treatment visit

The treatment phase is defined as the time between the study entry and the last dose of study treatment received within this trial. After confirming eligibility through the screening process, patients will be scheduled for visit day 1 (D1) of treatment within 48 h after randomization.

In this first visit, medical history, including clinically significant diseases, surgeries, cancer history, and reproductive status will be recorded at baseline. In addition, all medications (e.g., prescription drugs, over-the-counter drugs, vaccines, herbal or homeopathic remedies, nutritional supplements) used by the patient within 7 days prior to initiation of study treatment will be recorded. Also, in this first visit D1, patients will be given the first dose of treatment and will be instructed how to take giredestrant or tamoxifen orally, daily at their homes during the following 14 days D2 to D15 (to finalize a total of 15 days of treatment).

To assess patient compliance with self-administration of study medication, site study staff will provide patients with detailed instructions and training for the handling and administration of study drugs. Patients will receive and should be instructed to complete a medication diary to record all relevant information during those days.

A second biopsy will be collected at the EoT (on day 15 or day 15 + 1), after last dose of study treatment is taken by the patient in the EoT visit. If a fresh post-treatment biopsy cannot be obtained within + 1 day from last day of treatment, treatment will be extended to 16 days and patients will be able to have surgery or biopsy the following day (be it D15 + 2 days).

If a mandatory procedure described in the protocol falls on a bank holiday and/or weekend, this procedure should be performed on the day before or after the holiday (i.e. within a period of ± 2 working days), with the exception of the post-treatment surgery or biopsy that must be performed on the last day of treatment or 1 day after last day of treatment.

All patients will be closely monitored for safety and tolerability during study treatment. Patients should be assessed for toxicity prior to any study treatment administration; dosing will occur only if the clinical assessment and local laboratory test values are acceptable. Refer to **Section 7** for more information regarding toxicities.

3.3.3 Treatment and study discontinuation

If at any time the constraints of this protocol are detrimental to the patient's health and/or the patient no longer wishes to continue with the protocol therapy, the study treatment should be discontinued and the reason(s) for discontinuation documented in the clinical records of the patient and corresponding case report form (CRF).

Patient's study treatment may continue until one of the following criteria applies:

- Any medical condition or AEs that according to the protocol or in the judgment of the investigator may cause severe or permanent harm or which rule out continuation of study drug.

*Note: See detailed criteria for study treatment discontinuation due to toxicity in **Section 7**.*

- General or specific changes in the patient's condition render the patient unacceptable for further treatment in the judgment of the investigator.
- Disease progression per investigator's assessment.
- Serious non-compliance with the study protocol.
- Death.
- Pregnancy during study treatment.
- Concomitant use of any other (non-protocol) anti-cancer therapy.
- Lost to follow-up.
- Patient withdraws consent.
- The study site or the Sponsor decides to close the study.

All patients must return for the end of study visit 28 days (+/-3 days) after the final dose of study treatment regardless of the reason for treatment discontinuation. Patients who experience disease progression or unacceptable toxicity will be treated as per local practice after the EoS visit. If a patient discontinues treatment before the EoT visit (that is, before finalizing 15 days of treatment), the collection of tissue and blood samples will be discussed with the study medical monitor and will only be collected if feasible and as soon as possible (from a breast biopsy or breast surgery).

Patients have the right to withdraw from the study at any time for any reason. Should a patient decide to withdraw, all efforts should be made to complete and report the observations as thoroughly as possible. The investigator should contact the patient or a responsible relative by telephone or through a personal visit to establish as completely as possible the reason for the

withdrawal. A complete final evaluation at the time of the patient's withdrawal should be made with an explanation of why the patient is withdrawing from the study. Patients deciding to prematurely discontinue study treatment should be asked if they still can be contacted for further information. The outcome of that discussion should be documented in both the medical records and in the CRF.

The investigator also has the right to withdraw patients from the study in the event of intercurrent illness, AEs, and treatment failure after a prescribed procedure, protocol violation, administrative reasons, or for other reasons. An excessive rate of withdrawals can render the study uninterpretable; therefore, unnecessary withdrawal of patients should be avoided.

3.3.4 End of study visit

Patients will attend the clinic again for an EoS visit 28 days (+/- 3 days) after last dose of study treatment is taken.

All AEs related to investigational medicinal product (IMP) will be followed up by the investigator until the event or its sequelae has resolved to baseline grade or better, the event is considered as stable by the investigator, the patient is lost to follow-up, or the patient withdraws consent. Every effort should be done to follow-up all serious adverse events considered to be related to study drug or trial-related procedures until an outcome can be reported.

During the study period, resolution of adverse events (with dates) should be documented on the Adverse Event eCRF and in the patient's medical record to facilitate source data verification. All pregnancies reported during the study should be followed until pregnancy outcome.

The EoS is defined as the last patient last visit, which takes place 28 days (+/- 3 days) after the last study dose is taken (or if patient ends treatment due to progression or any other reason listed in the previous section, or until premature termination of the study). This will be the last data collection point, and the last patient visit.

In addition, the Sponsor reserves the right to terminate this study at any time. Reasons for terminating the study may include, but are not limited to, the following:

- The incidence or seriousness of AEs in this or other studies indicates a potential health risk to patients.
- Patient enrollment is unsatisfactory and/or excessively slow.
- Data recording is inaccurate or incomplete.
- Poor protocol adherence.
- Non-compliance with the International Conference on Harmonization (ICH) guideline for Good Clinical Practice (GCP).

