7.2 Safety profile and management of AEs for IMPs

AEs will be collected from the first study-mandated procedure until the End of Study visit to be done 28 days (± 3 days) after the last day of study treatment. All study subjects/patients will be carefully monitored for the occurrence of AEs during this period.

Clearly related signs, symptoms and abnormal diagnostic procedure results should be grouped together and reported as a single diagnosis or syndrome whenever possible. Any additional events that fall outside this definition should also be reported separately.

All AEs must be recorded in the CRF. The investigator should follow each adverse event until the event has resolved to baseline grade or better, the event is assessed as stable by the investigator, the patient is lost to follow-up, or the patient withdraws consent. Every effort should be made to follow all serious adverse events considered to be related to study drug or trial-related procedures until a final outcome can be reported.

Table 5. Guidelines for Management of Patients Who Experience Adverse Events Associated with Giredestrant (GDC-9545).

Adverse Reaction	Event action to be taken
Elevation of hepatic transaminases	
General guidance	
 If patient presents with jaundice, coagulopathy, abdominal pain, or other symptoms suggestive of hepatic toxicity, perform liver function tests with additional evaluation per institutional guidelines. If hepatic enzymes are elevated with no obvious malignant cause found, consult with hepatologist. Treat patient with hepatic enzyme elevation according to local standard of care.
Grade 1 or 2	
 Continue giredestrant (GDC-9545). Rule out alternative etiologies (e.g., disease progression, concomitant medications, or biliary obstruction). Treat patient according to local standard of care.
Grade 3	
 Permanently discontinue giredestrant (GDC-9545). Consult with hepatologist.
Grade 4 or meets criteria as defined by Hy's Law*	
 Permanently discontinue giredestrant (GDC-9545). Consult with hepatologist.
Gastrointestinal events (nausea, vomiting, diarrhea)	

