9. **AE reporting:** After informed consent has been obtained but prior to initiation of study drug, only serious adverse events caused by a protocol-mandated intervention should be reported with grading according to the NCI–CTCAE v.5.0 criteria. After initiation of study drug, all adverse events will be reported until 28 days (EoS) after the final dose of study treatment. After this period, the Sponsor should be notified if the investigator becomes aware of any serious adverse event that is believed to be related to prior study drug treatment.
10. **Concomitant medication reporting:** Medication (e.g., prescription drugs, over-the-counter drugs, vaccines, herbal or homeopathic remedies, nutritional supplements) used by a patient in addition to protocol-mandated treatment from 14 days prior to initiation of study drug until end of study visit.
11. **12-lead ECG:** Patients should be resting in a supine position for at least 10 minutes prior to ECG recording. All ECGs will be obtained prior to other procedures scheduled at that same time (e.g., vital sign measurements, blood draws). All patients must have a standard 12-lead ECG in screening period, maximum 48h before start of treatment dose, in the EoT visit and in the EoS visit.
12. **Laboratory assessments:** These values should include: hematological test (hemoglobin, hematocrit, red blood cell count, platelet count, WBC and differential count [ANC, lymphocytes, monocytes, eosinophils and basophils, and other cells]); coagulation (INR, PTT (or aPTT)); chemistry panel (serum or plasma): sodium, potassium, chloride, glucose, BUN or urea, creatinine, total protein, albumin, phosphate, calcium, total bilirubin (if total bilirubin is 2xULN, also direct bilirubin), AST, ALT, ALP, urate and LDH; fasting lipid panel: cholesterol, LDL cholesterol, HDL cholesterol, and triglycerides (after ≥ 8 hours of fasting); urinalysis, including dipstick (pH, specific gravity, glucose, protein, ketones, and blood) and microscopic examination (sediment, RBCs, WBCs, casts, crystals, epithelial cells, and bacteria), FSH and estradiol. Baseline (Day 1, prior to initiation of study treatment) laboratory assessments are not required if the screening assessments were performed at within 14 days prior to initiation of study treatment.

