4.5.2 Adverse Events

The adverse events will be tabulated per arm containing the number and percentage of subjects with the following:

- Subjects with at least one Adverse Event; and number of reported adverse events
- Subjects with at least one AE of special interest (AESI); and number of AESI
- Subjects with at least one Serious Adverse Events (SAEs); and number of SAEs
- Subjects with at least one AE related to the treatment; and number of AE related to the treatment
- Subjects with at least one SAE related to the treatment; and number of SAE related to the treatment

- Subjects who died due to SAEs; and number of SAEs that caused death
- Subjects that dropout due to SAEs; and number of SAEs that caused discontinuation
- Subjects with at least one treatment-emergent adverse event (TEAE); and number of reported TEAE. Adverse events starting or worsening during treatment phase will be considered as TEAEs.
- Subjects with at least one TEAE Grade ≥ 3 ; and number of reported TEAE Grade ≥ 3 .

The AEs will be also summarized according to the primary SOC and within each SOC, by PT according to the Medical Dictionary for Regulatory Activities (MedDRA). The duration of AE will be calculated as follows:

- Duration of an AE (days): (*date of resolution*) – (*start date*) + 1 when both end and start dates of AE are known and complete.

Missing data imputation methods

When data is not completed it will be considered as:

- Day 15 if day is missing
- Day 1 and month July if day and month are missing

In the event of not being able to allocate an AE, it will be considered as being a TEAE. Any missing information will be considered as being the worst case scenario (serious and treatment related).

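### The protocol gives two different scopes for following adverse events, and the SAP computes duration only when the end date is known, so any summary of AE duration will run short

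*Protocol*

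**What the plan says.** **Whose events are followed.** Protocol 3.3.4 states that "All AEs related to investigational medicinal product (IMP) will be followed up by the investigator until the event or its sequelae has resolved". Resolution there means a return to at least the baseline grade; follow-up also ends if "the event is considered as stable by the investigator, the patient is lost to follow-up, or the patient withdraws consent". SAP 1.5.4 repeats this text. Protocol 7.2 has a wider scope: "The investigator should follow each adverse event until the event has resolved to baseline grade or better", or until "the event is assessed as stable by the investigator, the patient is lost to follow-up, or the patient withdraws consent".

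**When data collection ends.** Of the EoS visit, 28 (±3) days after the last dose, Protocol 3.3.4 says: "This will be the last data collection point, and the last patient visit". Protocol 7.2 agrees on the collection window: "AEs will be collected from the first study-mandated procedure until the End of Study visit". Note 9 of Appendix 1 is similar: "After initiation of study drug, all adverse events will be reported until 28 days (EoS) after the final dose of study treatment". Sections 3.3.4 and 7.2.1 ask for resolution dates on the eCRF during the study period.

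**Other follow-up rules.** Protocol 7.2.1 follows SAEs and AESIs to resolution, stability or baseline condition. Protocol 5.5 follows AEs that interrupt or stop treatment to resolution or stabilisation. Neither depends on causality.

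**How duration is computed.** SAP 4.5.2 takes the resolution date minus the start date plus one, "when both end and start dates of AE are known and complete". It fills in partial dates (day 15 if the day is missing, 1 July if day and month are missing). It has no rule for an event with no end date.

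**The concern.** Two things looked wrong.

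First, a site with a non-serious AE judged unrelated and still ongoing at EoS gets different instructions from different sections. Section 7.2 tells it to continue follow-up. Section 3.3.4 names related events and is silent on this one.

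Second, the duration formula needs an end date. Among events that start on the same day, those unresolved at EoS are by construction the longer ones. Leaving them out shortens any mean or median of what remains. SAP 4.5.2 does not say how duration will be summarised, but the default in SAP 4.1 for continuous data includes both the mean and the median, so the shortening would carry into a reported table.

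At stake is a descriptive safety output: how long side effects last on each drug.

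**Working it through.** **1. The sections side by side**

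| Item | Protocol 3.3.4 / SAP 1.5.4 | Protocol 7.2 |
|---|---|---|
| Events named | IMP-related AEs | each AE |
| End conditions | resolved to baseline grade or better, stable, lost, consent withdrawn | the same |
| Data limit | EoS is the last data collection point | AEs collected to EoS |

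The conflict is one of scope; the stopping conditions match.

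**2. What reaches the duration formula under each reading**

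- *EoS closes data entry, under either scope:* every AE ongoing at EoS lacks an end date and is dropped, whatever its causality.
- *Scope of 7.2, later dates recorded:* events that resolve after EoS are kept. Those closed as stable, lost or withdrawn have no resolution date and are dropped. The shortening is smaller but does not vanish.
- *3.3.4 read as excluding unrelated AEs, later dates recorded:* related AEs that resolve after EoS keep their full length, while unrelated ones ongoing at EoS are dropped. Only here does the causality call matter. SAEs, AESIs and AEs that interrupt or stop treatment are outside it.

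**3. Size when EoS closes data entry**

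The plan states no figure for AE duration, so there is none to reproduce. Inputs:

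- From the documents: 15 days of treatment and EoS 28 days after the last dose, so EoS falls on day 15 + 28 = 43 (days 40 to 46 with the ±3-day window).
- Assumed: onset uniform over days 1-15 and exponential duration with mean m. The formula's plus-one is ignored.

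The time from onset to EoS, L, is then uniform between 43 − 15 = 28 and 43 − 1 = 42 days.

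- Share unresolved: p = m(e^(−28/m) − e^(−42/m))/14
- Mean of resolved events: m − A/(1 − p), where A = m[(28 + m)e^(−28/m) − (42 + m)e^(−42/m)]/14

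For m = 14:

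- p = e^(−2) − e^(−3) = 0.13534 − 0.04979 = 0.0855
- A = 42 × 0.13534 − 56 × 0.04979 = 2.896
- Mean of resolved events = 14 − 2.896/0.9145 = 10.8 days

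The other means follow in the same way. A simulation of one million events per setting agrees and supplies the range for EoS at days 40-46.

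| True mean (days) | Resolved by day 43 | Mean of resolved (days) | Range, EoS day 40-46 | True median | Median of resolved |
|---|---|---|---|---|---|
| 7 | 99% | 6.7 | 6.6-6.8 | 4.9 | 4.8 |
| 14 | 91% | 10.8 | 10.4-11.3 | 9.7 | 8.5 |
| 28 | 71% | 14.0 | 13.1-14.8 | 19.4 | 12.3 |
| 60 | 44% | 15.9 | 14.7-17.1 | 41.5 | 14.9 |

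**4. Sensitivity to onset**

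AEs are collected up to EoS, so onset can fall after day 15. With onset uniform over days 1-43 and m = 14, L is uniform between 0 and 42:

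- p = (14/42)(1 − e^(−3)) = 0.317
- A = [14² − 14 × 56 × e^(−3)]/42 = 3.74
- Mean of resolved events = 14 − 3.74/0.683 = 8.5 days, against 10.8 above

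**The case against.** **Duration is not an endpoint.** The safety endpoint is incidence and severity. Duration is absent from SAP 2.5 and from Protocol 8.8, and no between-arm test of it is planned. This stands and limits the importance of the point. It does not make the computed durations correct.

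**The inputs are assumed.** The documents give no AE durations, and for short events the effect is slight: about 0.3 of a day at a true mean of 7. This also stands. The direction of the bias when EoS closes data entry does not depend on the exponential shape; the size does.

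**Stronger reading: open-label causality calls bias the comparison of arms.** A reader might infer this, since investigators know the arm and judge relatedness. With a true mean of 30 days in both arms and 70% against 50% of AEs assumed to be judged related, one can obtain means of 26.4 and 23.6 days. But that needs three things together: sites treat 3.3.4 as excluding unrelated AEs, which it does not say; dates after EoS are entered, although 3.3.4 calls that visit the last data collection point; and every related AE is followed to a resolution date, although 3.3.4 also allows it to close as stable. If sites follow 7.2, or if EoS closes data entry, the dependence on causality disappears.

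**Kaplan-Meier as an unused method.** A reader might also infer that the Kaplan-Meier method described in SAP 4.1 has no endpoint. The exploratory sections listed in the SAP contents are not in the available text, so this cannot be concluded.

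**Conclusion.** The point holds in two parts. Protocol 3.3.4 (with SAP 1.5.4) and Protocol 7.2 conflict on which AEs are followed beyond EoS, and whether later resolution dates are recorded is left unclear. Separately, SAP 4.5.2 drops AEs without a known end date, so a duration summary can be expected to run short under either scope, and aligning the protocol sections alone would not cure that.

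If EoS closes data entry, and under the assumed onset and duration pattern, the shortfall in the mean is about 4% at a true mean of 7 days (0.3/7), 23% at 14 days (3.2/14) and 50% at 28 days (14.0/28). It would be larger if many AEs start after day 15, and smaller if resolution dates after EoS are captured. No trial-specific figure can be computed.

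A difference between arms driven by causality calls is possible only under the narrow combination of conditions described above and should not be presented as a consequence of the plan. Incidence, severity and the Ki67 analyses are unaffected. This is a minor point.

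**What to change.** 1. **Protocol 3.3.4, Protocol 7.2 and SAP 1.5.4:** reconcile these into one follow-up scope, and state whether resolution dates after EoS are entered in the database. Which scope to adopt is for the sponsor to decide.
2. **SAP 4.5.2:** report per arm the number of AEs unresolved at EoS. State how the partial-date rule fits with the requirement that dates be known and complete.
3. **SAP 4.5.2, if duration is summarised:** treat unresolved AEs as censored at EoS (or at last contact if earlier), for related and unrelated AEs alike. Kaplan-Meier is one suitable method and relies on non-informative censoring. If duration is not to be summarised, the count in item 2 is enough.

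The cost is a protocol clarification, a few lines in the SAP and one table. No extra visits and no change in sample size are needed. Reported durations would tend to be longer. The rule should be fixed before database lock so that it is not chosen after the data are seen.
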